9.6 Treatment Compliance

The calculation of overall compliance will be based on the planned SC administrations of CSL312 with complete volume and the planned dose:

$$\text{Treatment compliance (\%)} = 100 * (\text{Number of injections with complete volume administered} / \text{Total planned number of injections}).$$

The planned number of injections will be derived from the length of the subject's Treatment Period and the assigned dosing regimen. It will be calculated as:

For ongoing or discontinued subjects:

Q1M: Planned number of injections = floor[Duration of Treatment Period (days) / 30] + 1.

Q2M: Planned number of injections = floor[Duration of Treatment Period (days) / 30]/2 + 1.

For completed subjects:

Q1M: Planned number of injections = floor[Duration of Treatment Period (days) / 30].

Q2M: Planned number of injections = floor[Duration of Treatment Period (days) / 30]/2.

The number of planned injections will be rounded down to the next integer.

The following summaries will be provided for the Enrolled Analysis Set (see [Section 5.2](#)):

- Percentage overall compliance (descriptive statistics).
- Percentage overall compliance categorized by < 80%, 80%-120%, and > 120% (number and percentage of subjects in the categories).
- Number of injections not administered with reasons as per categories in the eCRF.
- Number of injections administered which deviate from the complete volume.
 - Reasons for not administering the planned volume with the categories in the eCRF.

A by-subject listing with the following information will be provided:

- Number of injections deviating from the planned volume.
- Planned and actual dosing regimen.
- Overall compliance.

10 Safety Analyses

Safety analyses will be based on the Safety Analysis Set (see [Section 5.3](#)).

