A Unscheduled visits (for safety evaluations, ie, to follow up on an adverse event) may take place at any point during the study per investigator discretion and / or per subject request.

B The Follow-up Visit may be conducted via telephone instead of at study site. Assessments / tests may be omitted if the Follow-up Visit is conducted via telephone. The Follow-up Period in this study is not applicable for subjects who choose to continue to receive CSL312 (and meet the criteria to participate in a post-study access program) or another prophylactic treatment. Subjects who do not choose the post-study access program or another prophylactic treatment will complete the Follow-up Visit as mandated in this study.

C Screening may be extended up to 60 days with permission from the sponsor. If the subject is not eligible for enrollment after 60 days, they will be screen failed or rescreened with permission from the sponsor (each subject may be rescreened a maximum of 1 time).

D No CSL312 administration takes place at End of Treatment. The last dose of CSL312 is administered at Month 10 (for subjects ages 2 to 5 years). Subjects who complete the study have the option to continue to receive access to CSL312 for a limited duration if they meet the criteria for the post-study access program. Any post-study access to CSL312 will be subject to the terms and conditions of the post-study access program. For these subjects, the Follow-up Period in this study will not be applicable. Subjects who do not choose the post-study access program or another prophylactic treatment will complete the Follow-up Visit as mandated in this study.

E Treatment Period visits have  $\pm$  4-day window, with a maximum of 64 days between any 2 consecutive doses.

F Written informed consent must be provided before any study-specific assessments or procedures are performed.

G Subjects may enter the open-label Treatment Period upon meeting all the inclusion and none of the exclusion criteria.

H A full physical examination will be conducted per the study site's standard procedure.

I Height will be collected at Screening Visit, Month 6 Visit, and End of Treatment Visit only.

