8.2 Protocol Deviations

A protocol deviation occurs when an investigator site, or study subject, does not adhere to protocol-stipulated requirements. Deviations will be assessed by CSL as they are reported and evaluated periodically during study conduct. All identified protocol deviations throughout the study will be listed prior to DBL and will be classified as minor or major by CSL. Major protocol deviations are defined as deviations that could have a significant effect on the subject's safety, rights, or welfare and/or on the integrity of the study data. All protocol deviations will be listed.

The protocol deviations' classification into minor and major will be reassessed under statistical considerations. Under statistical considerations, protocol deviations leading to exclusion from an analysis set will be considered major. Protocol deviations not leading to exclusion from an analysis set will be considered minor. The classification of protocol deviations under statistical considerations, the subject's assignment to analysis sets, and the occurrence of intercurrent events (ICEs) will be discussed in detail during the PARM based on by-subject listings provided for the PARM. The decisions made during the PARM will be documented in the pre-DBL Planned Analysis Review Report prior to DBL for final analysis. After DBL, the PARM listings will be re-run on database locked data, and it will be checked/confirmed that no changes which may have an impact on the assignment of subjects to analysis sets or ICEs occurred. The final assignment of subjects to analysis sets will be documented in the post-DBL Planned Analysis Review Report.

Table 4 **Potential Protocol Deviations and/or Reasons for Exclusion From Analysis Sets**

Potential Protocol Deviations/Reasons for Exclusion	Potential Exclusion From Analysis Set
Subject did not provide informed consent and/or informed consent date missing	Screened, Enrolled, Safety, PP, PK, PD
Subject enrolled but not treated with IP	Safety, PP, PK, PD
Subject treated but with wrong dosing regimen	PP
Subject treated but does not have at least one measurable PK concentration after IP administration	PK
Subject treated but does not have at least one PD measurement	PD
Subject violated inclusion and/or exclusion criteria	Enrolled, PP, (Safety, PK, PD)
Subject treated but compliance outside 80-120%	PP, (PK, PD)
Subject treated but received prohibited concomitant medication	PP, (PK, PD)

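### SAP 9.6 miscounts planned injections for completers with a Treatment Period under 360 days, and for adherent subjects who stop at a due date after one to three doses

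*SAP*

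**What the plan says.** SAP 9.6 divides the number of full-volume injections by a planned number. On the planned number it states: "The planned number of injections will be derived from the length of the subject's Treatment Period and the assigned dosing regimen".

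- Completed subjects: for Q2M, "Q2M: Planned number of injections = floor[Duration of Treatment Period (days) / 30]/2"; for Q1M, the same expression without the division by 2.
- Ongoing or discontinued subjects: "Q1M: Planned number of injections = floor[Duration of Treatment Period (days) / 30] + 1" and "Q2M: Planned number of injections = floor[Duration of Treatment Period (days) / 30]/2 + 1".
- The result is rounded down to an integer.

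SAP Table 3 and SAP 9.3 define the duration as EoT date minus first-dose date plus 1. Table 3 also resets a late EoT date to the last dose plus 30 days (Q1M) or plus 60 days (Q2M).

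The protocol's schedules (1.3.1 and 1.3.2) put EoT at Day 361 ± 4 and the last dose at Month 10 (Q2M) or Month 11 (Q1M). That makes 6 and 12 injections. Footnote D of 1.3.1 says: "No CSL312 administration takes place at End of Treatment".

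SAP Table 4 lists "Subject treated but compliance outside 80-120" per cent as a potential reason for exclusion from the PP set and, in brackets, from the PK and PD sets.

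**The concern.** The number of doses due by 12 months is fixed by the schedule, yet the SAP rebuilds it from the calendar length of the period. The result can therefore move with the day of the EoT visit even when dosing does not change. The protocol allows EoT up to four days early, and rounding down can then lose a dose. For subjects who stop early, the added 1 counts a dose at the end of the period, even when the subject attends only to finish.

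Two outputs are at stake. One is the compliance summary and by-subject listing. The other is the set of children flagged to the Planned Analysis Review Meeting (PARM) as possible exclusions. The PP set is used to repeat the attack-rate endpoint and its supplementary analyses (SAP 9.2.1). The target is about 20 subjects with at least 15 completers, so one child is about 1/20 = 5% of the sample.

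**Working it through.** **Inputs.** D is the Treatment Period length in days, equal to the EoT day number when no reset applies. Scheduled doses are 12 (Q1M: Days 1, 31, …, 331) and 6 (Q2M: Days 1, 61, …, 301). The EoT window is Day 357 to 365. The longest dosing gap is 34 days for Q1M (protocol 1.3.2); for Q2M the protocol says "with a maximum of 64 days between any 2 consecutive doses" (1.3.1). I read a late EoT as one more than 34 or 64 days after the last dose.

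**Nominal completer, D = 361.** Q1M: floor(361/30) = 12. Q2M: 12/2 = 6. Both match the schedule, so full dosing reads 100%.

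**Completers across the window.**

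| EoT day | Regimen | Planned | All doses taken | One dose missed |
|---|---|---|---|---|
| 357-359 | Q1M | floor(D/30) = 11 | 12/11 = 109.1% | 11/11 = 100% |
| 357-359 | Q2M | floor(11/2) = 5 | 6/5 = 120.0% | 5/5 = 100% |
| 360-365 | Q1M | 12 | 12/12 = 100% | 11/12 = 91.7% |
| 360-365 | Q2M | 6 | 6/6 = 100% | 5/6 = 83.3% |

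The rows for Days 360-365 assume no reset.

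**Completers with a reset.**

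- Last dose four days early (Day 327 for Q1M, Day 297 for Q2M) and EoT on Day 362-365: the gap exceeds 34 or 64 days. D becomes 327 + 30 = 357 or 297 + 60 = 357, and full dosing again reads 109.1% or 120.0%.
- Final dose missed and EoT on Day 361, with the child recorded as a completer: the last dose was on Day 301 or 241. D becomes 331 or 301, planned is 11 or 5, and compliance reads 100%.

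**Discontinued subjects with all k doses taken on nominal days.** The next dose is due on Day 30k + 1 (Q1M) or 60k + 1 (Q2M).

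- Period ends before Day 30k or 60k: planned = k, so compliance is 100%.
- Period reaches Day 30k or 60k: planned = k + 1, so compliance is k/(k + 1).

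| k | 1 | 2 | 3 | 4 | 5 |
|---|---|---|---|---|---|
| Compliance | 50.0% | 66.7% | 75.0% | 80.0% | 83.3% |

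At exactly D = 30k or 60k the formula counts a dose not due until the following day.

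The reset leads to the same place. The last dose falls on Day 30k - 29 (Q1M) or 60k - 59 (Q2M), so the reset sets D to 30k + 1 or 60k + 1. Any on-schedule discontinuer with a late EoT visit therefore reads k/(k + 1).

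**The case against.** Much of the case on the other side stands.

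- **Most completers are unaffected.** A reader might infer that on-time completers in general read 109% or 120%. They do not: Days 360 to 365 give 100% without a reset.
- **Completer errors move nobody out of the PP set.** SAP 9.6 places 120% in the middle category and Table 4 flags only values outside 80-120%. The correct values after one missed dose, 92% and 83%, are also inside the range.
- **Missed doses are not lost.** SAP 9.6 tabulates injections not given, with reasons, and SAP 10.1 lists them by subject. Only the percentage masks them.
- **Exclusion is not automatic.** A reader might infer that compliance decides PP membership. Table 4 describes its exclusions as potential, and the decision belongs to the PARM. However, the PARM receives a compliance listing (SAP 8.2), so it would start from the wrong figure.
- **The examples fall on scheduled dosing days.** Day 31 or 61 is a planned dosing day, and the no-dose footnote is written beside the Month 10 or 11 last dose. Counting a due dose that was not given is a defensible convention for an ongoing subject. It fits poorly for a child who has stopped: protocol 7.2 asks for the EoT assessments at withdrawal, and the dosing window is still open for four days. It cannot be defended at D = 30k or 60k, before the dose is due.

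**Conclusion.** The defect is real but confined to identifiable cases.

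- **Completers:** the planned number is one too low on three of nine permitted EoT days, and after a reset that brings the period below 360 days. The effect is on the compliance table and listing only.
- **Discontinued subjects:** a false value below 80% needs one to three doses, all taken, and a period that reaches the next due day. Mid-interval stops read 100%, and four or more doses read at least 80%. An affected child becomes a candidate for exclusion from the PP set, and possibly from PK and PD.

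The planned numbers imply about 20 - 15 = 5 non-completers, so few children can be affected. The false low values fall only on subjects who have not completed. It would be tempting to say that this biases the PP attack rate toward children who stayed. The documents do not show that: the PARM may keep these children, and the PP analysis is a descriptive repeat of a secondary endpoint.

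The figures assume doses on nominal days unless stated, 30-day months as in the formula, and the reading of a late EoT given above.

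**What to change.** - **Completers:** set planned injections to 12 (Q1M) or 6 (Q2M) from the Schedule of Activities, whatever the EoT day or reset. Full dosing then reads 100% on every day from 357 to 365. One missed dose reads 91.7% or 83.3%, including a missed final dose after a reset.
- **Discontinued or ongoing subjects:** count the scheduled dosing days whose +4-day window closed before the period end. Add any scheduled dose actually given in a window still open at that date. Do not count a dose at the EoT Visit. A Q1M child with three doses whose period ends on Day 91 then has 3 planned and reads 100%. One dosed on Day 31 who stops on Day 33 has 2 planned and reads 100%.

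A single expression such as ceil((D - 5)/30) or ceil((D - 5)/60) should not be used as a shortcut. For the child dosed on Day 31 who stops on Day 33 it gives ceil(28/30) = 1 planned, hence 2/1 = 200%. After a reset with the final dose missed it gives ceil(326/30) = 11 or ceil(296/60) = 5, so compliance still reads 100%.

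The cost is a few lines of SAP text and derivation code. No study procedure changes.

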10.1 Extent of Exposure

Exposure to the IP will be descriptively summarized by dosing regimen and overall:

- Duration of exposure (months and years) per subject.
- Number of SC administrations per subject.
- Total dose received (mg) per subject.

In addition, the following will be provided by dosing regimen and overall:

- Overall duration of exposure (total subject years).
- Overall number of SC administrations.

By-subject listings of individual subject data will include all variables presented in the summary tables and in addition details collected in the eCRF:

- Start and end date/time of the administration,
- Duration of the administration,
- Reason why an administration was not done
- Reason why the planned volume was not administered,
- Actual and planned volume and dose,
- Kit number,
- By whom the injection was administered,
- To which anatomical location the injection was administered.

10.2 Adverse Events

AEs will be coded using the MedDRA dictionary. There will be periodic updates of the MedDRA version. The latest licensed version will be used, and version updates will be implemented upon availability. AEs will be primarily classified by MedDRA PT. Analyses will be performed by SOC and PT. Aggregated incidences at SOC level and any TEAE will also be provided.

TEAEs are AEs that start on or after the date (and time if available) of the first administration of IP until the Follow-up Visit. TEAEs until the Follow-up Visit will be summarized. Subjects who continue with CSL312 or another prophylactic treatment after this study will not enter into the Follow-up Period and thus only TEAEs until the EoT are reported.

For the primary estimand, the TEAEs will be summarized until the EoT Visit (see [Section 10.2.1](#)).

All AEs regardless of whether they were treatment-emergent or not will be listed.

COVID-19-associated AEs will be included in TEAE tables identified by standard MedDRA coding.

Subjects with multiple occurrences of the same TEAE will be counted once in the total of those experiencing this PT. Similarly, a subject with 1 or more PT in a SOC will be counted once in the total of those experiencing PTs in that SOC. Percentages for subject incidence rates will be based on the Safety Analysis Set.

Injection site reactions (ISRs) will be summarized by an additional (artificial) "SOC" called "Injection Site Reactions". To identify PTs belonging to this (artificial) "SOC" of ISRs, CSL will be provided a list in Excel format of all PTs found in the database with verbatim. CSL will review this list and mark the corresponding PTs in a column of this Excel sheet. These identified PTs will be reported in the (artificial) "SOC" of ISR as well as in their original MedDRA SOC. For the overall "Any TEAE" entry at the beginning of the table, these ISRs will be reported once. ISRs will be presented as first "SOC" following the overall "Any TEAE" entry. The MedDRA SOC and PTs will be presented in descending frequency of the overall category. Within the same frequency, SOC and PTs will be ordered alphabetically.

Where AE start dates and/or times are missing or partially missing, AEs will be assumed to be treatment-emergent, except if the partial start dates and/or times or the AE end date and/or time indicate that the AE started before the first administration of IP (see [Table 5](#)).

Table 5 TEAE Assignment in Case of Missing AE Start Date Elements

Missing elements of AE start	Rule	
Regardless of any missing information for AE start: AE end date / time < IP start date / time		non-TEAE
Otherwise (i.e., if AE end date / time \geq IP start date / time)		
- All		TEAE
- Day and Month	AE start year \geq IP start year	TEAE
	AE start year < IP start year	non-TEAE
- Day	AE start month / year \geq IP start month / year	TEAE
	AE start month / year < IP start month / year	non-TEAE
- Time	AE start date \geq IP start date	TEAE
	AE start date < IP start date	non-TEAE

If AE start dates or end dates are missing or partially missing for an AE, no duration will be calculated. If for a TEAE the relationship to study treatment is missing the worst case will be assumed for summarizing analysis (i.e., the relationship to study treatment will be assumed to be "Related"). In case of missing study treatment relationship for non-treatment-emergent AEs, the relationship will be set to "Not related".

Temporally associated TEAEs are defined as AEs with an onset between the start of the injection and up to 24 hours after the end of the injection. In the case the time of the onset of the AE is missing, the AE is considered temporally associated, if the onset of the AE is between the day of the start of injection and the day of the end of injection + 1 day (inclusive). If the start date of the AE is (partially) missing the temporally association cannot be assessed.

Severe hypersensitivity including anaphylaxis is defined as AESI per study protocol . In addition to AESIs reported by Investigators per study protocol, events suggestive of any hypersensitivity including anaphylaxis will be identified for further review by:

- Standardised MedDRA Query "Hypersensitivity (SMQ)" (broad).
- Anaphylactic reaction (SMQ) (broad).
- Anaphylactic/anaphylactoid shock conditions (SMQ) (broad).

The broad scope includes narrow and broad search. The SMQ search does not account for severity (also non-severe cases will be included) while the AESI assessment by the investigator will do.

TEAE rates per subject year of exposure will be calculated as:

$$\text{TEAE rate per subject year} = \frac{\text{Number of TEAEs}}{\text{Subject Years of Exposure}}$$

where subject years of exposure will be the sum of the exposure duration in years for all subjects under this dosing regimen or overall. For the time exposed to a dosing regimen, each study day will be counted under the corresponding dosing regimen.

TEAE rates per injection will be calculated as:

$$\text{TEAE rates per injection} = \frac{\text{Number of TEAEs}}{\text{Number of Injections}}$$

where number of injections will be the sum of injections subjects received during the Safety Evaluation Period (see [Table 3](#)) under the dosing regimen the TEAE is assigned to.

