5.3 Safety Analysis Set

The Safety Analysis Set comprises all subjects in the Enrolled Analysis Set who received at least 1 dose of investigational product (IP). The Safety Analysis Set will be analyzed using the treatment that the subject actually received.

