Efficacy: Second 6 Months	Month 6 (Day 181) Visit Date + 1 day	Month 12 (Day 361) EoT Visit Date. If the EoT Visit of a subject is delayed by more than the treatment time window relative to the last IP administration, EoT Visit date will be set to last IP administration + 30 days or + 60 days for Q1M or Q2M, respectively.	End Date – Start Date + 1
Safety: First 3 Months	Date of first IP	EoT date if subjects discontinued or date of first IP + 90 if subjects is ongoing	End Date – Start Date + 1
Safety: Second 3 Months	End Date of previous 3- Months' Time Window + 1	EoT date if subjects discontinued or start date + 90 if subjects is ongoing	End Date – Start Date + 1
Safety: Third 3 Months	End Date of previous 3- Months' Time Window + 1	EoT date if subjects discontinued or start date + 90 if subjects is ongoing	End Date – Start Date + 1

Time Window	Start Date	End Date	Duration
Safety: Fourth 3 Months	End Date of previous 3-Months' Time Window + 1	EoT date if subjects discontinued or start date + 90 if subjects is ongoing	End Date – Start Date + 1
Safety: Fifth 3 Months (if applicable)	End Date of previous 3-Months' Time Window + 1	EoT date if subjects discontinued or start date + 90 if subjects is ongoing	End Date – Start Date + 1
...			

Note:

The first day of the Treatment Period may occur on the same day as the Screening Visit for subjects meeting the eligibility criteria for the study. In this case, the duration of the Screening Period is 0.

The Follow-up Visit is mandatory in this study unless a subject chooses to continue to receive CSL312 (and meet the criteria to participate in a post-study access program) or another prophylactic treatment. For these subjects, the Follow-up Period is not applicable.

The length of the month in the 3-Months' Safety time windows is set to 30 days.

8 Study Population

Unless otherwise stated, all tables and listings in this section will be presented by dosing regimen (100 mg Q2M and 100 mg Q1M) and overall.

Subjects who turn 6 years of age during the study will remain on their dosing regimen from study start and will be analyzed for the age group at their date of consent.

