10.2.2 Analysis of Primary Safety Endpoint

Following the estimand described in [Section 10.2.1](#), the TEAEs for pediatric subjects with C1-INH HAE will be summarized by event rate per subject year using the Safety Analysis Set. All summary tables described will be presented by 100 mg Q2M, 100 mg Q1M, and overall.

In addition, TEAEs will be summarized by the number of subjects and percentage of subjects experiencing at least 1 TEAE, the number of events, as well as the event rate per injection.

For the presentation by 3-months' time windows, the TEAE will be allocated to the time window based on the TEAE start date.

An overview summary of TEAEs as well as a table by SOC and PT will be provided.

The overview summary of TEAEs will include the following:

- Any TEAE.
- TEAEs related to IP.
- TEAEs related to device issues.
- Treatment-emergent ISRs.
- Treatment-emergent ISRs related to IP.
- Treatment-emergent ISRs related to device issues.
- Temporally related TEAEs occurring within 24 hours after end of administration.
- TEAEs leading to study discontinuation.
- TEAEs leading to discontinuation of study treatment.
- TEAEs by severity and relationship to IP and to device issues.
- TEAEs by outcome.
- Treatment-emergent ISRs by severity and relationship to IP and to device issues.
- Treatment-emergent AESIs as reported by the investigator (severe hypersensitivity including anaphylaxis).
- TEAEs by SMQ search (hypersensitivity including anaphylaxis).
- Treatment-emergent AESIs and TEAEs by SMQ search (hypersensitivity including anaphylaxis) related to IP and to device issues.
- Any serious TEAEs.

To evaluate the COVID-19 impact on the primary endpoint, the overview summary of TEAEs and the summary table by SOC and PT will be repeated as a sensitivity analysis excluding all COVID-19 related TEAEs (selected by "COVID-19 (SMQ)" scope "narrow").

All AEs will be presented in a by-subject listing.

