10.2.3 Analysis of Secondary Safety Endpoints

TEAEs

The following descriptive tables will be generated for TEAEs until the Follow-up Visit, including number and percentages of subjects, the number of events, and the TEAE rates per subject year of exposure and per injection:

- Overview table of TEAEs (same as described above, but until the Follow-up Visit).
- Overview table of serious TEAEs (same as described above, , but until the Follow-up Visit and restricted to serious TEAEs).
- TEAEs by SOC and PT (same as described above, but until the Follow-up Visit).
- TEAEs by SOC and PT by 3-months' time windows.
- TEAEs by SOC, PT, and severity.
- Related TEAEs by SOC and PT.
- TEAEs leading to study discontinuation by SOC and PT
- Treatment-emergent TEAEs related to clinically significant laboratory abnormalities by SOC and PT.
- Non-serious TEAEs by SOC and PT.
- Treatment-emergent AESIs and TEAEs by SMQ search (hypersensitivity including anaphylaxis) by SOC and PT.
- Related treatment-emergent AESIs and TEAEs by SMQ search (hypersensitivity including anaphylaxis) by SOC and PT.
- Serious TEAEs by SOC and PT.
- Related serious TEAEs by SOC and PT.

The following listings will be provided:

- TEAEs.
- Non-treatment-emergent AEs.
- SAEs.
- SAEs resulting in death.
- Related TEAEs.
- AEs leading to study withdrawal.
- AEs leading to permanent discontinuation of study treatment.
- AESIs and TEAEs by SMQ search (hypersensitivity including anaphylaxis).

Anti-CSL312 Antibodies

Number and percentages of subjects with total and neutralizing anti-CSL312 antibodies will be provided by study visit.

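### In the 3-month-window TEAE table, percentages on the full Safety Analysis Set count children no longer observed as event-free, which dilutes any fifth window and, if children leave the study, windows 2 to 4

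*SAP*

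**What the plan says.** SAP 10.2 gives a general rule for TEAE tables: "Percentages for subject incidence rates will be based on the Safety Analysis Set". Protocol 9.4.3 contains the same rule. SAP 5.3 defines the set as enrolled subjects with at least one dose, so membership is fixed from the first injection.

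SAP 10.2.3 lists the descriptive tables to be produced up to the Follow-up Visit, "including number and percentages of subjects, the number of events, and the TEAE rates per subject year of exposure and per injection". One of them is "TEAEs by SOC and PT by 3-months' time windows". For that presentation SAP 10.2.2 states that "the TEAE will be allocated to the time window based on the TEAE start date".

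Table 3 in SAP 7.4 defines the safety windows. From the second window on, the end is "EoT date if subjects discontinued or start date + 90 if subjects is ongoing". A fifth window is foreseen, marked as conditional.

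SAP 10.2 also says that "Subjects who continue with CSL312 or another prophylactic treatment after this study will not enter into the Follow-up Period", and that only their TEAEs up to End of Treatment (EoT) are reported.

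Elsewhere the SAP does restrict the population. SAP 9 limits each 6-month efficacy window to subjects who completed it. SAP 9.2.1.5 does the same for the Day 31 window. SAP 10.3 bases the percentages for clinically significant laboratory findings on subjects with non-missing values at the visit.

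**The concern.** A child can enter a window's numerator only by having a TEAE that starts in that window, and so only while under observation. The same child stays in the denominator of every window. Once observation ends, the child is counted as event-free, although nothing is known.

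A table by time window invites comparison across its columns. If fewer children are observed in later columns, a constant proportion with events prints as a decline, which could be read as improving tolerability. The study is small and SAP 10.2.2 splits its tables by regimen, so single children carry weight: one unobserved child removes 1/20 = 5% of the denominator overall, and 1/10 = 10% within a regimen if the two are of equal size (an assumption).

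**Working it through.** The plan states no figure to reproduce: there is no hypothesis test, and the sample size was agreed with health authorities. The check follows the stated rules.

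**Inputs from the documents**
- About 20 enrolled, at least 15 completing 12 months (SAP 3; protocol 4.1).
- Window = start to start + 90, which is 91 days inclusive: Days 1–91, 92–182, 183–273, 274–364, 365–455 (SAP Table 3).
- EoT at Day 361 (protocol 1.3.1 and 1.3.2).
- Last dose at Month 10 for Q2M (Day 301) and Month 11 for Q1M (about Day 331). Follow-up Visit 3 months after the last dose, taken as 90 days.

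**Assumptions**
- Constant true risk *p* of at least one TEAE per fully observed window: 40%, with 20% and 60% as a range.
- Losses of 0, 2 or 5 of 20, spread evenly.
- Number entering Follow-up: anything from 0 to 20.

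**Formula.** With *N* children in the Safety Analysis Set and *m* observed in the window, the expected number with an event is *p* × *m*. The printed percentage is therefore *p* × *m*/*N*; among observed children it is *p*.

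**Windows 1 to 4, *p* = 40%, *N* = 20**

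| Lost | Observed *m* | Printed % | % among observed |
|---|---|---|---|
| 0 | 20 / 20 / 20 / 20 | 40 / 40 / 40 / 40 | 40 throughout |
| 2 | 20 / 19 / 19 / 18 | 40 / 38 / 38 / 36 | 40 throughout |
| 5 | 20 / 18 / 17 / 15 | 40 / 36 / 34 / 30 | 40 throughout |

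For example, window 4 with 5 lost is 40 × 15/20 = 30. At *p* = 20% and 60% the same cell is 20 × 15/20 = 15 and 60 × 15/20 = 45. If 15 of 20 are still observed, the relative understatement is 1 − 15/20 = 25%. With no loss it is zero.

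The table ignores one small effect. A child who leaves at Day 361 is seen for 361 − 274 + 1 = 88 of 91 days in window 4, which under a constant hazard lowers the risk from 40% to 1 − 0.6^(88/91) ≈ 39%.

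**Window 5, effect of the denominator.** A child with EoT at Day 361 and no Follow-up Period contributes 0 days from Day 365. The factor *m*/20 is 20/20 = 1 if all 20 enter Follow-up, 10/20 = 0.5 if 10 do, 5/20 = 0.25 if 5 do, and 0 if none do. None of this requires dropout.

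**Window 5, effect of partial observation.** Children in Follow-up are not seen for the whole window either.
- Q2M: visit at 301 + 90 = Day 391, so 391 − 365 + 1 = 27 days.
- Q1M: visit at 331 + 90 = Day 421, so 421 − 365 + 1 = 57 days.

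At a constant hazard equivalent to 40% per 91 days, the risks are 1 − 0.6^(27/91) ≈ 14.1% and 1 − 0.6^(57/91) ≈ 27.4%. With regimens split equally the average is about 20.7%. On the full Safety Analysis Set this prints as 20.7 × 10/20 ≈ 10.4% if 10 of 20 enter Follow-up, and as 20.7% if all 20 do. Changing the denominator removes the step from 20.7% to 10.4%. It does not remove the step from 40% to 20.7%, which only person-time can handle.

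**The case against.** The strongest case against runs as follows.

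- **The full safety set is the usual denominator.** For whole-period tables this is correct. A reader might infer from the general wording of the rule that all TEAE percentages are faulty; they are not. The problem is confined to one secondary descriptive table. The primary summary, TEAE rate per subject year up to EoT, does not use this denominator.
- **The decline is not automatic.** A reader might infer that percentages must fall across all windows. In windows 2 to 4 they fall for this reason only if children leave observation. Stopping treatment is not the same thing: protocol 7.1 keeps such children in the study for data collection. Fifteen completers of 20 is a minimum target, not a forecast, and a rising true risk could hide the dilution.
- **The large fifth-window figures are hypothetical.** A reader might take a quarter or a half of the true value as established. The documents do not say how many enter Follow-up, and if all do the denominator causes no dilution. The end rule for that window refers to EoT or start + 90 and does not mention Follow-up, although SAP 10.2.3 runs these tables to the Follow-up Visit.
- **The same table shows event counts and rates.** SAP 7.4 says that its time windows serve the TEAE analysis and gives each a duration, which leans towards window-level exposure. SAP 8.1 reports how many skip Follow-up because they continue prophylaxis. This helps an attentive reader. But the rate definitions in SAP 10.2 use exposure duration and injections over the Safety Evaluation Period without saying that they are split by window, and correct rates would not correct the percentage beside them.
- **The table shells may already print a per-window n.** They are a separate document and cannot be checked here. If they do, the SAP sentence should be brought into line.
- **The laboratory rule is an imperfect parallel.** Laboratory values are present or missing at a visit, whereas AEs accrue continuously. This stands, and it is why a changed denominator needs observed time alongside it.

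**Conclusion.** The point holds for the 3-month-window table. As written, its subject percentages equal the percentage among observed children times the fraction observed, and no provision in either document overrides this.

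In windows 2 to 4 the understatement is zero without loss, and 25% relative in window 4 if only 15 of 20 are still observed. In a fifth window it is built into the schedule, and its size is unknown: none if all 20 enter Follow-up, half if 10 do. The 40% risk, the loss pattern and the Follow-up uptake are illustrations; the multiplication by the observed fraction does not depend on them.

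The documents do not support the inference that TEAE percentages are unsound in general, that a falling profile is guaranteed, or that the primary safety result is affected. Nor would a new denominator alone make the fifth window comparable with the others: under a constant 40% risk it would still show about 21%, given 27 or 57 observed days of 91 and an equal split of regimens.

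**What to change.** In SAP 10.2 and 10.2.3, for the 3-month-window table only:

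1. Base subject percentages on Safety Analysis Set children with at least 1 day of AE observation in that window. The end of observation can be taken from the Safety Evaluation Period in Table 3; the window end rule should be aligned with it, since the tables run to the Follow-up Visit.
2. Print that n and the observed subject-time for each window, by regimen and overall.
3. State that the per-subject-year and per-injection rates in this table use observation time and injections within the window.
4. State that the partially observed fifth window is to be compared with earlier windows on those rates, not on percentages.

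Keep the full Safety Analysis Set for all whole-period TEAE tables. Because protocol 9.4.3 carries the same general rule, record the exception in SAP Section 4.

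The cost is a few SAP sentences and added header counts in one table shell. No new data are needed, and the change can be made before database lock.
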